## 6 STUDY PROCEDURES

The image consists of a series of horizontal black bars of varying lengths and positions on a white background. The bars are irregular in shape, with some having sharp edges and others being more rounded. They are arranged in a non-linear fashion, with some bars appearing to overlap or be positioned above or below others. The overall effect is one of a digital signal or a heavily processed image where the original content has been abstracted into these basic geometric shapes.

## 7 ADVERSE EVENTS AND ADVERSE DEVICE EVENTS

[figure not shown]
[figure not shown]
[REDACTED]

Cutera, Inc.

Protocol # C-17-TS16

"Multi-Center Pilot Study of truSculpt Device"

---

## 7.2 Recording AEs/ADEs and SAEs/SADEs

All AEs/SAEs or ADEs/SADEs will be: (1) evaluated and must be recorded in the subject's study case report forms (CRFs); (2) monitored and tracked from the time of the first treatment.

At each contact with the subject, the investigator must seek information on AEs/ADEs/SADEs by specific questioning and, as appropriate, by examination. AEs/ADEs/SADEs may be observed by the investigator and/or clinical research staff, elicited from the subject and/or family member or volunteered by the subject. All observed and volunteered adverse signs and symptoms, anticipated or unanticipated, regardless of severity or frequency, will be recorded in the case histories (medical chart and CRFs). Included in the description should be the nature of the sign or symptom, the date of onset, date of resolution (duration), the severity, anticipated or unanticipated, the relationship to study treatment or other therapy, the action taken (if any), and the outcome.

All SAEs/SADEs, anticipated or unanticipated, must be reported to Cutera immediately but not later than 5 working days. The SADE must be recorded in: (1) the CRF and (2) a written report must be submitted to Cutera within five (5) working days after the investigator first learns of the event and is to include a full description of the event and sequelae, in the format detailed by the Cutera Serious Adverse Event Form

### 7.3 Follow-up of Subjects after AEs

All reported AEs/ADEs/SAEs/SADEs should be followed until resolution or until the subject's participation in the study ends. Resolutions of AEs/ADEs/SAEs/SADEs are to be documented on the appropriate CRFs. All ADEs that result in permanent discontinuation from this clinical trial, whether serious or not, should also be reported on the subject Non-Completion of Study Form.

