### 5.2.1 Subject Discontinuation Criteria

If possible, every subject should remain in the study until completion of the required follow-up period. However, participation in this study is completely voluntary and a subject can choose to withdraw from the study at any time. Decision to withdraw will not affect or prejudice the subject's continued medical care in any way. In those instances, the investigator will attempt to obtain a final clinical assessment and an adverse device effect evaluation for the subject prior to this withdrawal. A subject will be considered lost to follow-up only after three unsuccessful, documented attempts to contact the subject have been made.

In addition, a subject can be discontinued for any of the following reasons: the Principal Investigator decides that continuing in the study would not be in the subject's best interest, a subject is noncompliant with the protocol, a subject has a serious reaction to the treatment, a subject develops any of the exclusion criteria during the study period or the study is stopped by the study sponsor.

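### On the visible text, AE follow-up stops at study exit and a serious reaction may be the reason for that exit, so the event's later course may go unrecorded

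*Protocol*

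**What the plan says.** Section 7.3 gives one stopping rule for every class of event (AE, ADE, SAE, SADE): they "should be followed until resolution or until the subject's participation in the study ends". It makes no exception for serious or device-related events that are still open. It also foresees device effects that cause permanent exit, and for these it adds that they "should also be reported on the subject Non-Completion of Study Form".

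Section 5.2.1 starts from retention: "If possible, every subject should remain in the study until completion of the required follow-up period". It then deals with voluntary withdrawal and continues: "In those instances, the investigator will attempt to obtain a final clinical assessment", together with an "adverse device effect evaluation for the subject prior to this withdrawal". A separate list follows, opened by "In addition, a subject can be discontinued for any of the following reasons". One entry reads "a subject has a serious reaction to the treatment"; another is a stop by the sponsor. No assessment is attached to that list.

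Section 7.2 requires active questioning: "At each contact with the subject, the investigator must seek information on AEs/ADEs/SADEs by specific questioning". It says the description of an event should cover, among other items, its resolution date, severity and outcome. For a SADE it requires a written report, including sequelae, within five working days of the investigator's first knowledge. Section 4.1.1 names incidence and severity of adverse device events as the safety endpoint.

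**The concern.** Two written rules interact. One ends follow-up when participation ends. The other allows participation to end because of a serious reaction. The event of greatest safety interest can thus be the cause of its own cut-off. Any resulting error would run one way: an event that worsens or persists after exit would look milder or shorter than it was.

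The pilot has about 40 subjects and plans no formal testing (9.3), so the descriptive safety record is one of its main products, and a single incomplete serious case would be noticeable in it. This is also not something that can be left to a statistical analysis plan, because an outcome not collected at the time cannot be restored by later analysis.

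**Working it through.** No formula applies beyond one conversion of units, so the check sets the provisions side by side.

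**The chain**

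1. A serious reaction occurs and is unresolved.
2. Under 5.2.1 the subject can be discontinued for it. This is a permission, not an obligation.
3. If that permission is used, participation ends.
4. Under 7.3 the duty to follow the event then ends, whether or not it has resolved.

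**How far each visible safeguard reaches**

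- Retention default (5.2.1): lowers the chance of step 3, but applies only where possible, and the same section lists the exceptions.
- Final assessment (5.2.1): attempted only, made before the exit, and tied by its opening words ("In those instances, the investigator will attempt to obtain a final clinical assessment") to voluntary withdrawal. The list containing serious reaction and sponsor stop comes afterwards and mentions none.
- Questioning at each contact (7.2): works only if a contact takes place. No visible text requires one after exit.
- Written SADE report (7.2): captures the event and the sequelae known within five working days of first knowledge. No follow-up report is visible.
- Non-Completion of Study Form (7.3): records that the event led to exit, not its later course.

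None of these visibly requires information after exit.

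**What is kept and what may be lost**

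- Kept: that the event occurred, its severity up to exit, its status at exit, and sequelae known at the time of the SADE report.
- May be lost: final outcome, resolution date, and worsening after exit.

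**Effect on the section 9.4 table**

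Section 9.4 reports how many subjects, and what share, had each AE term. Exit does not change whether a subject is counted. The instruction to take the worst severity and greatest length serves to avoid counting a repeated event twice. The severity entry can change only if an event was below grade 3 at exit and worsened later, because grade 3 is the top of the scale in 4.3.2. If the analysis set in 9.2 (subjects who complete treatment) also governs safety, only exits after completed treatment affect the table. The gap in the recorded data applies to any subject who leaves with an open event.

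**Time at stake**

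- Exit just after the final treatment: follow-up is planned at 12 weeks after it (sections 4 and 4.1.2), so up to 12 × 7 = 84 days may be lost.
- Earlier exit: the loss can be longer, since section 4.2 puts participation at about 10 months. The number of treatments and their spacing are redacted, so no closer figure can be given.

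The protocol gives no rate of serious reactions, of discontinuation or of worsening after exit, so the expected number of affected subjects cannot be calculated.

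**The case against.** The strongest reply is that the protocol contains no error here. Following events to resolution or to the end of participation is a clear, workable rule, and an open event can be recorded as ongoing at exit. A reader might infer that 7.2, which asks for resolution date and outcome, contradicts 7.3. It does not, for that reason. What stands against the reply is that the stated rule gives least information on the events that matter most, and this is cheap to improve.

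A second reply is redaction. Section 6, whose contents list includes a follow-up visit (6.3), section 7.1 and the study schedule cannot be read, and any of them may deal with early exit. A reader might infer that the protocol has no provision after exit at all. The visible text cannot support that. It does show that 7.3 states its rule without an exception or a cross-reference.

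A third reply is that removal is a decision and need not be immediate. This is correct. To say that a serious reaction ends its own follow-up would be too strong; it may do so if the investigator uses the permission in 5.2.1 while the event is open.

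Finally, the link to the endpoint is thin. A reader might infer that incidence is understated or that the duration wording in 9.4 biases the results. Neither follows: incidence is captured, outcome and resolution date are not part of the endpoint in 4.1.1, and the 9.4 summary is a count of subjects. Only severity below grade 3 at exit is exposed.

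**Conclusion.** The point holds as a limited gap in data collection. On the visible text, 7.3 ends follow-up of open events at exit, 5.2.1 permits exit because of a serious reaction, and no visible safeguard reaches beyond exit. What may be lost is the final outcome, the resolution date and later worsening.

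The effect on the 9.4 table is small. The overall size of the loss cannot be derived; only a time can be given, up to 12 weeks for exit just after the final treatment and more for earlier exit. The 84 days are therefore not an upper limit for every subject.

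The conclusion assumes that no redacted section already requires follow-up after exit, and that the final assessment in 5.2.1 refers, as its position suggests, to voluntary withdrawal. Confidence is medium for these two reasons. The change should be made as an inexpensive improvement to the safety record; it does not correct a contradiction.

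**What to change.** Reconcile 5.2.1, 7.2 and 7.3 as follows:

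- State that discontinuation does not by itself end safety data collection.
- Unless consent is withdrawn, record the status, severity and outcome of open serious events, and of open device- or procedure-related events, through the follow-up contact already planned.
- Report events still unresolved then as ongoing at last contact. Some will still lack a resolution date, but the cut-off will no longer depend on the decision to discontinue.
- Apply the final assessment in 5.2.1 to investigator- and sponsor-led discontinuation as well.

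If a redacted section already says this, a cross-reference in 7.3 is enough.

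The cost is a few sentences of wording and a few extra contacts with subjects who leave with an open event. The change concerns data collection only; it alters neither who is discontinued nor how an event is treated.

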## 8 POTENTIAL RISKS / BENEFITS

A 16x4 grid of black bars on a white background. The bars vary in length and position. The first row has a short bar at the top. The second row has a small bar in the middle. The third row has a long bar with a white gap. The fourth row has a medium bar. The fifth row has a long bar. The sixth row has a medium bar. The seventh row has a short bar. The eighth row has a medium bar. The ninth row has a short bar. The tenth row has a medium bar. The eleventh row has a short bar. The twelfth row has a medium bar. The thirteenth row has a short bar. The fourteenth row has a large, dark, jagged bar. The fifteenth row has a medium bar. The sixteenth row has a short bar.

## 8.2 Potential Benefits

The subjects may or may not benefit from the treatment with the study device. Potential benefit is improved appearance of treated area. There is no guarantee of success.

## **9 DATA ANALYSIS PLAN**

### **9.1 Sample Size**

This is an exploratory pilot study and 40 subjects has been deemed appropriate for evaluation of the device.

### **9.2 Analysis Sets**

The analysis sets will include all enrolled subjects who complete treatment.

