#### 4.1 Study Endpoints

##### 4.1.1 Safety Endpoint

- Incidence and severity of adverse device events.

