##### 4.1.2 Exploratory Endpoints

- [REDACTED]

- GAIS at 12 weeks post first and final treatment from Baseline.

- [REDACTED]

- [REDACTED]

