### **9.4 Safety Analyses**

Device-related and procedure-related adverse effects (AEs) will be tabulated and analyzed. For a given AE term, counting will be done by subject, not by event, i.e. for a subject reporting the same AE more than once, the event will be counted only once, at the most severe and longest duration. The number and percentage of subjects experiencing each AE Term will be descriptively summarized.

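### Section 9.2 restricts every analysis set to subjects who complete treatment, so a treated subject stopped early for a device event drops out of the safety table

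*Protocol*

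**What the plan says.** The whole of Protocol section 9.2 is one sentence: "The analysis sets will include all enrolled subjects who complete treatment". It speaks of sets in the plural and puts the same completion condition on all of them.

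The only named safety endpoint (section 4.1.1) is "Incidence and severity of adverse device events". Section 9.4 describes its analysis: "The number and percentage of subjects experiencing each AE Term will be descriptively summarized". Each subject counts once per term, at the worst severity and longest duration. Section 9.4 names no population of its own, and sections 9.1 to 9.4, all legible, give no set other than the one in 9.2.

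Three other places bear on who would be excluded:

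- Section 5.2.1 lists among the reasons for discontinuing a subject that "a subject has a serious reaction to the treatment".
- Section 7.3 sends to the Non-Completion of Study Form "All ADEs that result in permanent discontinuation from this clinical trial, whether serious or not".
- Section 7.2 has adverse events "monitored and tracked from the time of the first treatment".

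The number of treatments is redacted, but section 4.1.2 sets an endpoint of "GAIS at 12 weeks post first and final treatment from Baseline", so a course of more than one session is possible.

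**The concern.** A safety population should be fixed by exposure. Here it is fixed by completion, and completion can itself depend on the outcome being measured. A subject who has a first treatment, reacts badly and is stopped before the course is finished has been exposed and has had an event, yet does not meet the condition in 9.2.

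The reported incidence then describes people who tolerated the device well enough to finish. Severity is affected in the same way when the events that stop treatment are the worse ones. The protocol also works against itself: it collects adverse events from the first treatment onward, then defines an analysis population that leaves some of them out.

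What is at stake is the only safety result the study will produce. Section 9.3 plans no formal testing for the efficacy and exploratory endpoints, and the safety output is a table of counts and percentages. The denominator of that table therefore matters, and with about 40 subjects one or two exclusions can remove a whole category of event.

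**Working it through.** **Plan's own figure.** The planned size is 40: "This is an exploratory pilot study and 40 subjects has been deemed appropriate for evaluation of the device". No event rate, precision target or dropout rate is given, so there is no calculation to reproduce. Only N = 40 comes from the protocol. Every event and dropout count below is an assumption.

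**Notation.** N = subjects treated; E = those with a given event; D = treated subjects who do not complete treatment; d = those among the D who had the event.

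- Incidence among all treated: E/N.
- Incidence under section 9.2: (E − d)/(N − D).

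**Direction.** The second is below the first when N(E − d) < E(N − D), that is, when Nd > ED, or d/D > E/N. The plan understates incidence exactly when non-completers have a higher event rate than all treated subjects. When subjects are stopped because of an event, d/D is near 1 and the condition is met. When they leave for unrelated reasons it need not be.

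**Illustration 1: events stop treatment.** N = 40, E = 4, D = d = 2, with exact (Clopper-Pearson) 95% intervals:

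| Quantity | All treated | Section 9.2 set |
|---|---|---|
| Any event | 4/40 = 10.0% (2.8 to 23.7%) | 2/38 = 5.3% (0.6 to 17.7%) |
| Severe event, if the 2 stopped subjects are the only severe cases | 2/40 = 5.0% (0.6 to 16.9%) | 0/38 = 0% (0 to 9.3%) |

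**Illustration 2: range over d.** N = 40, E = 4 (10.0% among all treated), D = 4:

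| d | Section 9.2 result |
|---|---|
| 0 | 4/36 = 11.1% |
| 1 | 3/36 = 8.3% |
| 2 | 2/36 = 5.6% |
| 3 | 1/36 = 2.8% |
| 4 | 0/36 = 0% |

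**Illustration 3: the other direction.** N = 40, E = 7, D = 8, d = 1. Here d/D = 1/8 = 12.5%, below E/N = 7/40 = 17.5%. The plan reports 6/32 = 18.8%, which is too high.

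**Does the text let this happen?** The answer depends on what completing treatment means, which the legible text does not say.

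- *Completing the planned course.* Anyone stopped between sessions, or during one, is excluded.
- *Completing any one session.* A subject stopped between sessions stays in. A subject whose first or only session is cut short by an event is still excluded.

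Some loss remains under both readings. Subjects who finish treatment and withdraw during follow-up are unaffected under either.

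**The case against.** The strongest objection is that the harm is conditional and modest. The key term is undefined in the legible text, the study procedures are blacked out, and the number of treatments may vary by subject. On the lenient reading only an interrupted first or only session is lost. This is right about the extent, which could be small, but it does not remove the defect.

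The link from 9.2 to 9.4 is also an inference: 9.4 names no population, and 9.2 says what the sets include without adding that nobody else belongs. However, 9.2 is the only definition offered and covers the sets collectively, so an analyst following the protocol has no other denominator. A statistical analysis plan may exist, but 9.2 does not leave the matter open for it. A plan with an all-treated safety set would contradict the protocol.

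Section 7.3 concerns leaving the trial, which can happen after the last treatment, so it is supporting evidence only. Section 5.2.1 gives no timing either, but nothing confines its serious-reaction reason to the period after treatment is complete.

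Finally, this is a pilot without formal testing. Events are still recorded on case report forms, serious ones must reach the sponsor within 5 working days, and no visible stopping rule uses the 9.4 percentages. All of that stands. It means that case-level capture of harm is intact and that the fault lies in the summary table. That table is still the study's stated safety result.

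**Conclusion.** The concern holds and should be corrected before analysis. As written, section 9.2 makes completion of treatment a condition for entering the safety summary, while section 5.2.1 allows a subject to be discontinued because of harm. The rule is stated in the protocol, so this is not a gap left for a later document.

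The size is unknown. In the assumed cases with 4 events among 40 treated, a true 10.0% is reported anywhere from 0% to 11.1%, depending on how many of 4 non-completers had an event. A 5.0% rate of severe events can be reported as zero. The bias is downward when exclusions are driven by events and can be upward when they are not.

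The conclusion rests on 9.2 governing 9.4, which is the only reading the legible text supports. It also rests on at least one treated subject failing to complete treatment. If everyone treated completes, the two populations coincide and nothing changes.

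**What to change.** In section 9.2, define a safety set of every subject who receives any part of at least one study treatment, and state that all of section 9.4 uses it. State in the same place what completing treatment means for any set that keeps that condition.

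Beside the adverse-event table, give the number of treated subjects who did not complete treatment, with the reason for each. For GAIS, a completer summary can stay if the number treated and the number missing are shown with it. No imputation is required.

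The cost is one or two sentences for the safety set, plus the line defining completion. No new data, visits or subjects are needed: adverse events are already recorded from the first treatment, and discontinuations for adverse device effects already go on the Non-Completion of Study Form. The only downside for the sponsor is that reported event rates may look slightly less favourable.

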### 4 STUDY DESIGN

This is a multi-center, pilot study in approximately 40 subjects, ages 18 to 65. Subjects may receive [REDACTED] treatments and will be followed at 12 weeks post [REDACTED] final treatment.

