#### 4.2 Study Duration

Subjects enrolled in this trial will be asked to participate for approximately 10 months, depending on treatment(s).

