## 4.3 Study Assessments

### 4.3.1 Exploratory Assessments

Investigators will complete an assessment of the device along with the Global Aesthetic Improvement of the subjects from baseline vs. 12 weeks post first and last treatment.

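### The completer-only analysis set in Section 9.2 does not fit the GAIS endpoint taken 12 weeks after the first treatment

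*Protocol*

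**What the plan says.** Section 9.2 states the population for every analysis in a single sentence: "The analysis sets will include all enrolled subjects who complete treatment". The readable text names no other set.

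Section 4.1.2 lists "GAIS at 12 weeks post first and final treatment from Baseline" as an exploratory endpoint, and the Protocol Summary repeats it. Section 4.3.1 has investigators assess the "Global Aesthetic Improvement of the subjects from baseline vs. 12 weeks post first and last treatment". The post-first grade is thus an endpoint separate from the post-final one.

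On treatment, Section 4 says: "Subjects may receive [REDACTED] treatments and will be followed at 12 weeks post [REDACTED] final treatment". Section 4.2 puts participation at roughly 10 months, varying with the treatments received.

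On stopping, Section 5.2.1 says that "a subject can choose to withdraw from the study at any time". It also allows discontinuation for several reasons, among them that "the Principal Investigator decides that continuing in the study would not be in the subject's best interest". When a subject withdraws, the investigator is to try to obtain a last clinical assessment.

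Section 9.1 sets the size by judgement: "This is an exploratory pilot study and 40 subjects has been deemed appropriate for evaluation of the device". Section 9.3 plans no formal hypothesis testing.

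**The concern.** What a first treatment achieves is a question about everyone who received one. Under Section 9.2, a subject who is treated once, is graded 12 weeks later and then leaves a planned course does not count towards that answer, although the grade exists. Entry to the post-first summary is decided by something that happens after the first treatment.

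That later event may be related to the grade. A subject who sees no change, or who found treatment unpleasant, has a reason to stop; a satisfied subject may also see no need to go on. Investigators complete the GAIS and can also discontinue a subject on their own judgement, so the grade and the decision can share an assessor.

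The readable design describes no control group in which the same selection would operate. With no testing planned, the descriptive summary is the efficacy output, and its denominator settles what it means. With about 40 subjects, a handful of exclusions visibly moves a percentage.

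**Working it through.** **The plan's own figure.** The only relevant figure is 40 subjects. It has no alpha, power, effect size or dropout rate behind it, so there is nothing to reproduce.

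**Step 1: does the rule discard valid grades?** Set Section 9.2 beside Section 4.1.2. Naming both a first and a final treatment presupposes more than one treatment for at least some subjects. For such a subject, grading 12 weeks after the first treatment does not require completing the course, but entry to the analysis set does. The grade can exist and be excluded.

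**Step 2: can the grade come before completion?** The visit schedule is not readable, so this can only be checked against duration.
- 10 months = 10 × 365.25 / 12 / 7 = 43.5 weeks.
- Less the 12-week follow-up after the final treatment: 43.5 − 12 = 31.5 weeks.
- Less an assumed 4 weeks of screening: 27.5 weeks.

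Both exceed 12 weeks, so the post-first grade can fall before the final treatment. This shows that the order is possible, not that it is the order planned.

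**Step 3: how far could the result move?** Let p be the share improved 12 weeks after the first treatment among all first-treated subjects, and c1 and c0 the completion rates of improved and non-improved subjects. The share seen in completers is

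p·c1 / (p·c1 + (1 − p)·c0).

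The values of p, c1 and c0 are assumptions; the protocol gives none of them. The improved/non-improved split is only a device for the illustration, since the readable text defines no such cut on the GAIS. With p = 0.50 and 40 first-treated subjects:

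- c1 = 0.90, c0 = 0.90: 0.450 / 0.900 = 50.0%, 36 analysed, no shift.
- c1 = 0.95, c0 = 0.75: 0.475 / 0.850 = 55.9%, 34 analysed, +5.9 points.
- c1 = 0.95, c0 = 0.60: 0.475 / 0.775 = 61.3%, 31 analysed, +11.3 points.
- c1 = 0.70, c0 = 0.95 (satisfied subjects stop): 0.350 / 0.825 = 42.4%, 33 analysed, −7.6 points.

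These are illustrations, not limits. A sharper contrast, c1 = 0.90 and c0 = 0.50, gives 0.450 / 0.700 = 64.3%, +14.3 points.

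**Step 4: without assuming a direction.** Suppose 6 of 40 do not complete and 19 of the 34 completers improved (55.9%). If none of the 6 improved, the share in all 40 is 19/40 = 47.5%. If all 6 improved, it is 25/40 = 62.5%. The completer figure alone cannot separate these.

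**Step 5: after the change.** If all first-treated subjects are graded and kept, the expected share is p, and selection on later completion is gone. Any remaining selection comes from grades never obtained, so the missing count has to be shown.

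**The case against.** The strongest objection is that the mechanism rests on text that cannot be read. The number of treatments, the procedures and the schedule are blacked out, and no definition of completing treatment is visible. The wording of Sections 4 and 4.2 suggests that the number of treatments varied by subject. If a single planned treatment counts as completion for some subjects, their post-first grades are kept and the discarded group shrinks. This stands, and it limits the point to subjects planned for more than one treatment.

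The timing argument is also soft. The Protocol Summary runs from first enrolment in August 2017 to last visit in May 2018, so 10 months is close to a ceiling and later enrollees must have less. If the final treatment came before the first grade, that grade could not influence completion. This stands too. Even so, the grade of a subject who stopped early would still be excluded, and reasons for stopping, such as discomfort, could still be related to it.

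It may be said that Section 9.2 does not use the word only, and that a SAP could define endpoint-specific sets. But completer-only is the natural reading of a sentence covering all the sets. A SAP using all first-treated subjects would depart from what the protocol fixes. This is a stated rule that does not fit an endpoint, not detail left for later.

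Finally, this is an exploratory pilot without formal testing, so no error rate, power or decision rule is affected. That is right and bounds the consequence.

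A reader might infer more: that the post-first result is bound to look too good, or that a poor first grade is known to drive dropout. The documents support neither. The order of grade and completion is inferred from duration, and satisfied subjects stopping early would push the result the other way.

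**Conclusion.** The point holds as a mismatch between a stated analysis set and a stated endpoint. As written, Section 9.2 drops valid post-first GAIS grades from subjects planned for more than one treatment who later stop, and so conditions the post-first summary on a later event that may be related to it.

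The size and direction of the bias cannot be derived from the protocol. The illustrative range of about −8 to +11 percentage points rests wholly on an assumed 50% improved and assumed completion rates; with equal completion there is no shift. The consequence is confined to a descriptive summary. It is worth correcting because the remedy is small and that summary is how the efficacy objective is reported.

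**What to change.** In Section 9.2, define the set for the GAIS 12 weeks after the first treatment as all subjects who received the first treatment, using every grade obtained whether or not treatment was later completed. Report the numbers treated, graded and missing. Keep the completer set for the post-final GAIS, and show its count against the number first treated.

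No responder cut, and no rule counting ungraded subjects as not improved, is asked for, because the readable text gives no basis for splitting the scale.

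Adding a separate safety set alone would not repair this, since the GAIS population would remain completers.

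The cost is a short addition to Section 9.2 and one more denominator in the GAIS table, with no new visits, data or subjects. The reported result may be less favourable.
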